19.1 Appendix 1: Dysphagia Symptom Questionnaire (Paper and Electronic Versions)

Patient ID: _____ - _____ - _____

Date: _____

Dysphagia Symptom Questionnaire (DSQ)

Instructions

This daily diary includes questions about your Eosinophilic Esophagitis (EoE). We are interested in any trouble you had today swallowing foods such as meat, rice, fruit, bread, etc.
Please complete this questionnaire after you have had your last meal of the day.

Read each question and answer by selecting the box that best describes your experience. There are no right or wrong answers to any of the questions.

Question #1: During the past 24 hours, did you eat solid food?
	 No  Yes

Question #2: During the past 24 hours, has food gone down slowly or been stuck in your throat?
	 No  Yes

If you answered "Yes" to Questions 1 and 2, please proceed to answer Questions 3 and 4.
	

Question #3: For the most difficult time you had swallowing food today (during the past 24 hours), did you have to do anything to make the food go down or to get relief?
	 No, it got better or cleared up on its own  Yes, I had to drink liquid to get relief  Yes, I had to cough and/or gag to get relief  Yes, I had to vomit to get relief  Yes, I had to seek medical attention to get relief

Question #4: The following question concerns the amount of pain you have experienced when swallowing food: What was the worst pain you had while swallowing food during the past 24 hours?
	 None, I had no pain  Mild  Moderate  Severe  Very Severe

Allakos, Inc. Dysphagia Symptom Questionnaire v2.0

19.1 Appendix 1: Dysphagia Symptom Questionnaire cont.

< Back

Dysphagia Symptom Questionnaire
1/4

Instructions

This daily diary includes questions about your Eosinophilic Esophagitis (EoE). We are interested in any trouble you had today swallowing foods such as meat, rice, fruit, bread, etc.

Please complete this questionnaire after you have had your last meal of the day.

Read each question and answer by selecting the box that best describes your experience. There are no right or wrong answers to any of the questions.

Back
Next

Dysphagia Symptom Questionnaire
2/4

Since you woke up this morning, did you eat solid food?

No

Yes

Back
Next

19.1 Appendix 1: Dysphagia Symptom Questionnaire cont.

Dysphagia Symptom Questionnaire3/4

Since you woke up this morning, has food gone down slowly or been stuck in your throat?

Note (not shown):

If "NO" is answered to either Question # 1 or Question # 2 the questionnaire will be complete for that day and the subject will skip forward to the questionnaire submission screen (page 6 of 7 in this document).

If "YES" is answered to both Question # 1 and Question # 2, the remainder of the DSQ will populate and the subject will continue on to answer Question # 3 (page 4 of 7 in this document) and Question #4 (page 5 of 7 in this document) followed by questionnaire submission screen (page 6 of 7 in this document) and instructions to return to home screen (page 7 of 7 in this document)

19.1 Appendix 1: Dysphagia Symptom Questionnaire cont.

Dysphagia Symptom Questionnaire
4/6

For the most difficult time you had swallowing food today (during the past 24 hours), did you have to do anything to make the food go down or get relief?

No, it got better or cleared up on its own

Yes, I had to drink liquid to get relief

Yes, I had to cough and/or gag to get relief

Yes, I had to vomit to get relief

Yes, I had to seek medical attention to get relief

Back
Next

Dysphagia Symptom Questionnaire
5/6

The following question concerns the amount of pain you have experienced when swallowing food. What was the worst pain you had while swallowing food over the past 24 hours?

None, I had no pain

[figure not shown]
Mild

Moderate

Severe

Very Severe

Back
Next

19.1 Appendix 1: Dysphagia Symptom Questionnaire cont.

The screenshot shows the ViedocMe logo at the top center. Below it is a dark blue header bar with the text "Dysphagia Symptom Questionnaire" on the left and "6/6" on the right. Underneath the header, the text "4 of 4 questions answered" is displayed in orange. A paragraph of instructions follows: "Click 'Send' to submit the data. Please observe that you cannot go back and edit any submitted data. If you want to change some of your answers now, please click 'Back', change data and then submit the data." At the bottom of the interface, there are two buttons: a grey "Back" button on the left and a green "Send" button on the right.

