11.2 Pharmacodynamic/Efficacy-Related Procedures

11.2.1 Dysphagia Symptom Questionnaire

Throughout the duration of study participation (including screening period, treatment period, and follow-up period), subjects will self-administer an electronic version of the DSQ ([Appendix 1](#)) daily after the last meal of the day at approximately the same time each evening.

Subjects will not be able to complete a questionnaire more than 24 hours after it is due and will not be able to go back and make any corrections or changes to the data originally entered. This information will be automatically captured and maintained in the ePRO system of the EDC.

A paper version of the PRO questionnaire is available to subjects in case they are not able to complete the electronic version for a short period of time. Only one PRO should be completed per day, and the recall period should not be more than approximately 24 hours long. This information will be manually captured and entered into the EDC by the study site.

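### Paper and electronic DSQ put Questions 1 and 2 over different recall periods, and the co-primary score pools the two forms without distinction

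*Protocol*

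**What the plan says.** **Wording.** The paper form in Protocol 19.1 (Appendix 1), footed "Allakos, Inc. Dysphagia Symptom Questionnaire v2.0", asks Question 2 as "During the past 24 hours, has food gone down slowly or been stuck in your throat"; Question 1 has the same 24-hour lead-in. The electronic screens in the same appendix ask "Since you woke up this morning, did you eat solid food" and "Since you woke up this morning, has food gone down slowly or been stuck in your throat". The scoring table in Protocol 19.11 (Appendix 11), labelled version 4.0, uses the since-waking wording for both. The visible text of SAP 9.1 (Appendix 1) shows only the paper wording.

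**Completion.** Protocol 11.2.1 asks for the diary each evening after the last meal. Paper is a short-term back-up that the site keys into the database. For electronic entries, "Subjects will not be able to complete a questionnaire more than 24 hours after it is due"; the time at which an entry falls due is not stated.

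**Branching.** On paper, a Yes to both Questions 1 and 2 leads to Questions 3 and 4. The electronic note says that after a No to either question "the questionnaire will be complete for that day and the subject will skip forward to the questionnaire submission screen".

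**Scoring.** Question 2 scores 0 or 2 and Question 3 scores 0 to 4. Questions 1 and 4 do not enter the score. The biweekly score is the sum of points times 14, divided by the days reported (Protocol 19.11; formula repeated in SAP 9.1). SAP 5.4.2 uses every available day and sets no rule for mode or lateness.

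**The concern.** A paper day can count an episode from the previous late evening or night that an electronic day excludes, and both enter one 14-day score as if they were the same measurement. The wording that departs from the scoring table is the paper wording, and the SAP, which supersedes the protocol's statistical methods, shows that version.

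The score decides inclusion (criterion 3, at least 12; Protocol 7.3), the randomisation stratum (at most 30 or above 30; Protocol 10.2), the second co-primary endpoint, and secondary endpoints 4 to 7 in SAP Table 7. Paper use in screening is foreseen: Appendix 11 makes the automatic eligibility calculation conditional on all screening diaries being electronic. Without a flag for mode and entry date, there is no planned way to show that a DSQ result does not depend on mixed recall periods.

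Two related weaknesses are possible readings of the text:

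- The electronic note can be read as ending the diary on a No to Question 1, whereas paper asks Question 2 regardless.
- An electronic entry made after the next waking would, read literally, ask about the wrong day.

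**Working it through.** **1. The plan's own figure.** Inputs from SAP 3.6: difference 15 − 7.5 = 7.5, SD 15, power 90%; two-sided 0.05 from SAP 5.8. Normal approximation: 2 × (1.960 + 1.282)² × (15/7.5)² = 84.1, so 85 per group. The t-test solves to 85.03, so 86, as stated. Power at 86 is 90.6% (t-test 90.3%). 86/(1 − 0.14) = 100. The sample size reproduces and is not in dispute.

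**2. The forms side by side.**

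| Item | Paper | Electronic | Scoring table |
|---|---|---|---|
| Q1 (gate) | 24 hours | since waking | since waking |
| Q2 (scored, gate) | 24 hours | since waking | since waking |
| Q3 (scored) | today / 24 hours | today / 24 hours | today / 24 hours |
| Q4 (not scored) | 24 hours | 24 hours | 24 hours |

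The difference is confined to the first two rows.

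**3. One discordant day, one subject.** The shift is points × 14 / days reported.

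- 14 days reported: Question 2 alone gives 2 × 14/14 = 2; the maximum (2 + 4) gives 6.
- 7 days reported: 2 × 14/7 = 4; maximum 12.

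Two points take a score of 10 to 12 (eligible) or 30 to 32 (upper stratum). Reaching 6 requires a day scored zero under one form and, under the other, a day on which the subject sought medical attention.

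**4. Expected shift from paper wording.** Assume k paper days in one 14-day period only, an extra probability q of a Yes on a paper day, and 3 points per Yes day. Shift = k × q × 3. For k = 1 and q = 0.05 to 0.20 it is 0.15 to 0.6 points; for k = 2 it is 0.3 to 1.2. If paper use is equal by arm, this largely cancels in the between-arm difference.

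**5. Late entry.** Assume every subject reports one follow-up day twice and misses another, with independent days and daily SD s. The variance of the 14-day sum goes from 14s² to 12s² + 4s² = 16s², a rise of 2s².

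- s = 2: SD = √(225 + 8) = 15.26; power at 86 per group 89.7%.
- s = 1.5: SD = √(225 + 4.5) = 15.15; power 90.1%.
- s = 3: SD = √(225 + 18) = 15.59; power 88.4%.

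**6. A pessimistic bound.** If a discordant day carried no treatment information at all (SD held at 15), one such day in 14 gives a difference of 7.5 × 13/14 = 6.96 and 86% power; two give 7.5 × 12/14 = 6.43 and 80%.

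The documents give no rate of paper or late entries, so k and the one-day-per-subject scenario are assumptions.

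**The case against.** **The windows nearly coincide.** Both forms open by asking about trouble swallowing today and are to be completed after the last meal. If that is followed, the 24-hour window adds mainly the previous late evening and night, when little is eaten. Question 3 mixes both phrasings in every version, including the scoring table. This stands, and it limits the size. It does not make the two wordings of Question 2 the same.

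**Branching.** A reader might infer that a day with no solid food but food sticking scores 2 on paper and can never score electronically. The text does not establish this. The screen counters (2/4 and 3/4 for Questions 1 and 2, then 4/6 and 5/6 for Questions 3 and 4) suggest that Question 2 is always shown and only Questions 3 and 4 are gated, as on paper. The note permits either reading.

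**Late entry.** A reader might infer that one day is reported twice and another lost. That depends on when an entry is due, which is undefined, and on subjects ignoring which day the entry is for. Sites must also monitor diary compliance (Protocol Table 1, note 5).

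**Size.** It is tempting to set a 6- or 12-point individual shift against the planned difference of 7.5. That mixes an individual's worst case with a difference of group means. The bound in step 6 is also too harsh for a late entry, because an adjacent day of the same subject on the same treatment still carries treatment information.

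**Version labels.** A reader might take v2.0 on paper against version 4.0 in the scoring table to mean an outdated instrument. The documents do not say that the labels belong to one numbering series. Whether the 24-hour wording is psychometrically non-equivalent cannot be judged from them either.

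**Conclusion.** The wording mismatch in Questions 1 and 2 is real, affects a scored item, and has no safeguard in the SAP. It is a correctable defect of measurement and analysis planning. It does not invalidate the endpoint.

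For an individual with a full diary, the realistic shift is 2 points per discordant day, which matters mostly near the cuts at 12 and 30. For the comparison between arms, the likely result under blinded randomisation is non-differential noise. In the late-entry illustration, with one affected day for every subject, power falls by roughly 0.5 to 2 percentage points from 90.6%. This rests on assumed frequencies, on a daily SD of 1.5 to 3, and on similar paper and late-entry use in all arms. Nothing in the documents supports a claim of bias in favour of AK002 or of an inadequate sample size. The branching and late-entry points are ambiguities to close.

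**What to change.** 1. Reword paper Questions 1 and 2 to the since-waking wording of the electronic form and scoring table. State one rule for whether Question 2 is asked after a No to Question 1, and apply it in both forms. Replace the copy in SAP Appendix 1.
2. Show the named diary date on each electronic entry and define when an entry is due in Protocol 11.2.1, so that a late entry refers to its own day. A fixed midnight closure is not needed; it would exchange late entries for missing ones.
3. In the SAP, before unblinding, flag paper entries and entries made on the next calendar day in the analysis data set. Prespecify a repeat of the DSQ co-primary analysis without them as a sensitivity analysis.

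Cost: a minor form and ePRO update and one extra table. The sensitivity analysis will have fewer diary days, which the score already normalises. The sample size stays at 86 per group, or about 100 with dropout.

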19.2 Appendix 2: Solid Food Question (Paper Version)

Patient ID: _____ - _____ - _____

Date: _____

Solid Food Question

Instructions

You are being asked this question because you answered "No" to Question #1 of the Dysphagia Symptom Questionnaire (DSQ).
Please answer this question immediately after you have completed the DSQ.

Question:

Was EoE the primary reason that you did not eat solid food during the past 24 hours?

No

Yes

CCI

CCI

19.5 Appendix 5: EG/EoD PRO Questionnaire (Paper Version)

EOSINOPHILIC GASTRITIS AND DUODENITIS (formerly referred to as Gastroenteritis) DISEASE PATIENT-REPORTED OUTCOME QUESTIONNAIRE												

Instructions: This questionnaire asks about symptoms that people with eosinophilic gastritis (EG) and duodenitis (EoD) may have. Think of the last 24 hours and choose the number that best describes the intensity of your own EG and EoD symptoms during that time. Please complete the daily diary every day, at approximately the same time.
 
Please choose an answer by selecting only one box for each item. Answer all the items, do not skip any. If you are unsure about how to answer an item, please give the best answer you can.
												
1. Over the past 24 hours, please rate the intensity of your abdominal (stomach) pain at its worst.	0 	1 	2 	3 	4 	5 	6 	7 	8 	9 	10 	NO ABDOMINAL PAIN WORST POSSIBLE ABDOMINAL PAIN
2. Over the past 24 hours, please rate the intensity of your nausea (feeling like you have to throw up) at its worst.	0 	1 	2 	3 	4 	5 	6 	7 	8 	9 	10 	NO NAUSEA WORST POSSIBLE NAUSEA
3. Over the past 24 hours, please rate the intensity of your vomiting (throwing up) at its worst.	0 	0 	1 	2 	3 	4 	5 	6 	7 	8 	9 	NO VOMITING WORST POSSIBLE VOMITING
4. Over the past 24 hours, how many times did you vomit (throw up) ?	[patient to enter number]											
5. Over the past 24 hours, please rate the intensity of your fullness before finishing a meal at its worst.	0 	1 	2 	3 	4 	5 	6 	7 	8 	9 	10 	NO EARLY FULLNESS BEFORE FINISHING A MEAL COMPLETE FULLNESS BEFORE FINISHING A MEAL
6. Over the past 24 hours, please rate the intensity of your loss of appetite (not feeling hungry) at its worst.	0 	1 	2 	3 	4 	5 	6 	7 	8 	9 	10 	NO LOSS OF APPETITE COMPLETE LOSS OF APPETITE
7. Over the past 24 hours, please rate the intensity of your abdominal (stomach) cramping at its worst.	0 	1 	2 	3 	4 	5 	6 	7 	8 	9 	10 	NO ABDOMINAL CRAMPING WORST POSSIBLE ABDOMINAL CRAMPING

19.5 Appendix 5: EG/EoD PRO Questionnaire cont.


8. Over the past 24 hours, please rate the intensity of your bloating (stomach feels bigger or under pressure) at its worst.
	
 
 0	1	2	3	4	5	6	7	8	9	10	
 
 											
 
 NO BLOATING	WORST POSSIBLE BLOATING	
 
	0	1	2	3	4	5	6	7	8	9	10												NO BLOATING					WORST POSSIBLE BLOATING					
0	1	2	3	4	5	6	7	8	9	10																								
																																		
NO BLOATING					WORST POSSIBLE BLOATING																													

9. Over the past 24 hours, how many times did you have diarrhea (defined as type 6 or 7 stools on the Bristol Stool Chart)? Click for Bristol Stool Chart.
	
[patient to enter number]
																																	

10. Over the past 24 hours, please rate the intensity of your diarrhea (defined as type 6 or 7 on the Bristol Stool Chart) at its worst.
	
 
 0	1	2	3	4	5	6	7	8	9	10	
 
 											
 
 NO DIARRHEA	WORST POSSIBLE DIARRHEA	
 
	0	1	2	3	4	5	6	7	8	9	10												NO DIARRHEA					WORST POSSIBLE DIARRHEA					
0	1	2	3	4	5	6	7	8	9	10																								
																																		
NO DIARRHEA					WORST POSSIBLE DIARRHEA																													

19.5 Appendix 5: EG/EoD PRO Questionnaire cont.

Bristol Stool Chart

Type 1		Separate hard lumps, like nuts (hard to pass)
Type 2		Sausage-shaped but lumpy
Type 3		Like a sausage but with cracks on its surface
Type 4		Like a sausage or snake, smooth and soft
Type 5		Soft blobs with clear-cut edges (passed easily)
Type 6		Fluffy pieces with ragged edges, a mushy stool
Type 7		Watery, no solid pieces. Entirely Liquid

CCI

CCI

CCI

CCI

CCI

CCI

Thank you for completing these questions!

CCI

19.7 Appendix 7: Baseline Diet Assessment

Instructions: To be completed by Study Personnel, through direct interview with Study Participant. Please ask questions to Study Participants, much as they appear below. This Assessment should be conducted on Day 1 of the Screening Period.

1. Are you on Specific, Doctor-Prescribed Diet? Yes No

If Yes, what is the diet?

- Elemental [If ticked-enteral/tube feeding?] Yes No
- 6-food or 3 Food Elimination Diet
- Supplemental Protein Shake/drink specify: _____
- Other; describe: _____

2. Do you have any confirmed food allergies (i.e., confirmed by skin-prick testing or blood tests)? Yes No

If Yes, what are they? _____

3. Does eating certain foods seem to make your EoE worse? Yes No

If Yes, what are the 3 specific foods/types of foods that make the effects worse?

Food or Type of Food	Effect

4. Do you avoid eating any specific foods or types of foods due to your EoE? Yes No

If Yes, which foods are **always** avoided? _____

5. Do you avoid? (tick all that are appropriate)

- Milk
- Egg
- Wheat
- Soy

What are the main foods that YOU DO eat?

If a full diet is eaten do not list all types of foods, just write "All foods."

6. Do you avoid eating at certain times of the day to avoid symptoms of EoE? Yes No

If Yes, please describe: _____

19.8 Appendix 8: Common Terminology Criteria for Adverse Events (Version 5.0)

Common Terminology Criteria for Adverse Events (CTCAE) Version 5 for download can be found at: https://ctep.cancer.gov/protocolDevelopment/electronic_applications/docs/

CTCAE_v5_Quick_Reference_5x7.pdf

Example of Grading for Infusion-Related Reactions

Adverse Event	General Disorders and Administration Site Conditions				
	Grade 1	Grade 2	Grade 3	Grade 4	Grade 5
Infusion related reaction	Mild transient reaction; infusion interruption not indicated; intervention not indicated	Therapy or infusion interruption indicated but responds promptly to symptomatic treatment (e.g., antihistamines, NSAIDs, narcotics, IV fluids); prophylactic medications indicated for <24 hours	Prolonged (e.g., not rapidly responsive to symptomatic medication and/or brief interruption of infusion); recurrence of symptoms following initial improvement; hospitalization indicated for clinical sequelae	Life-threatening consequences; urgent intervention indicated	Death
Definition: A disorder characterized by adverse reaction to the infusion of pharmacological or biological substances.					

Example of Grading for Laboratory Abnormalities

Adverse Event	Grade				
	1	2	3	4	5
Growth hormone abnormal	Asymptomatic; clinical or diagnostic observations only; intervention not indicated	Symptomatic; medical intervention indicated; limiting instrumental ADL	–	–	–
Definition: A finding based on laboratory test results that indicate abnormal levels of growth hormone in biological specimen.					
Haptoglobin decreased	<LLN	–	–	–	–
Definition: A finding based on laboratory test results that indicate a decrease in levels of haptoglobin in a blood specimen.					
Hemoglobin increased	Increase in >0–2 g/dL	Increase in >2–4 g/dL	Increase in >4 g/dL	–	–
Definition: A finding based on laboratory test results that indicate increased levels of hemoglobin above normal.					
Lipase increased	>ULN –1.5 × ULN	>1.5–2.0 × ULN; >2.0–5.0 x ULN and asymptomatic	>2.0–5.0 × ULN with signs or symptoms; >5.0 x ULN and asymptomatic	>5.0 × ULN and with signs or symptoms	–
Definition: A finding based on laboratory test results that indicate an increase in the level of lipase in a biological specimen.					
Lymphocyte count decreased	<LLN–800/mm ³ ; <LLN–0.8 × 10e9/L	<800–500/mm ³ ; <0.8–0.5 × 10e9/L	<500–200/mm ³ ; <0.5–0.2 × 10e9/L	<200/mm ³ ; <0.2 × 10e9/L	–
Definition: A finding based on laboratory test results that indicate a decrease in number of lymphocytes in a blood specimen.					
Lymphocyte count increased	–	>4000/mm ³ –20,000/mm ³	>20,000/mm ³	–	–
Definition: A finding based on laboratory test results that indicate an abnormal increase in the number of lymphocytes in the blood, effusions, or bone marrow.					

19.9 Appendix 9: EGD Histology

Details for collecting, labeling, and shipping specimens will be provided separately.

Staining: The performance of the evaluations listed below will require the following stains for each biopsy set:

- Esophagus: 1) H&E; 2) tryptase; 3) trichrome
- Stomach: 1) H. pylori immunostain; 2) H&E; 3) tryptase; 4) trichrome
- Duodenum: 1) H&E; 2) tryptase; 3) trichrome

Biopsies will be obtained from the following:

- **Esophagus**

- A set of 2 fragments from the distal esophagus
- A set of 2 fragments from the mid-proximal esophagus.
- Up to 2 extra specimens may be collected if there are any additional areas of interest

A count of ≥ 15 eosinophils per hpf in at least one esophageal site will be considered diagnostic of eosinophilic esophagitis (EoE).

- **Stomach**

- A set of 4 specimens from separate areas of the gastric antrum (2–5 cm proximal to the pylorus)
- A set of 4 specimens from separate areas of the gastric corpus (two from the proximal lesser curvature and two from the greater curvature)
- Up to 2 extra specimens may be collected if there are any additional areas of interest

A count of ≥ 30 eosinophils per hpf in at least 5 hpf will be considered diagnostic of eosinophilic gastritis (EG).

- **Duodenum**

- 4 fragments of duodenal mucosa from the second and third part of the duodenum.
- Up to 2 extra specimens may be collected if there are any additional areas of interest

A count of ≥ 30 eosinophils per hpf in at least 3 hpf will be considered diagnostic of eosinophilic duodenitis (EoD).

Note: Any stored tissue from biopsies of the esophagus, stomach, or duodenum may be used for exploratory analysis.

19.9 Appendix 9: EGD Histology cont.

The following will be reported for esophageal biopsies:

- Maximum number of eosinophils per hpf
- Maximum number of tryptase-positive mast cells per hpf

In addition, the following histopathologic parameters will be graded from 0 (absent) to 3 (marked or severe):

- Eosinophilic microabscesses
- Eosinophilic degranulation
- Basal zone hyperplasia
- Spongiosis
- Subepithelial tissue present (Y/N)
- Lamina propria fibrosis (grade only if subepithelial tissue is present)

The following will be reported for gastric biopsies:

- Confirmation of absence of *H. pylori*. A highly sensitive monoclonal immunohistochemical stain will be used. If negative, then the subject can be included in the study and the following histopathologic parameters will be graded using the Sydney System from 0 (absent) to 3 (marked or severe) for all except eosinophil counts:
- Maximum number of eosinophils per hpf
- Maximum number of tryptase-positive mast cells per hpf
- Active inflammation
- Chronic inflammation
- Intestinal metaplasia
- Atrophy
- Reactive gastropathy

The following will be reported for duodenal biopsies:

- Maximum number of eosinophils per hpf
- Maximum number of tryptase-positive mast cells per hpf
- Duodenal intraepithelial lymphocytosis (with counts per 100 enterocytes when count is >20)
- Villous architecture

